7.3 STUDY SCHEDULE

Assessment/Procedure	Screening	Visit 1 (V1) (prior to vaccination)	Visit 2 (v2) (14 days post vaccination)	Visit 3 (V3) (6 months post vaccination)	Visit 4 (V4) (12 months post vaccination)
Study timeline	Day 0	Day 1	Day 14	Day 150	Day 330
Time window	-28 to 1d	NA	+7d	±30d	±30d
Informed Consent	X				
Collection of demographic information	X				
Weight and height measurement	X				
History of seasonal influenza vaccination	X				
Randomization	X				
Blood Collection	X ^a	X ^a	X	X	X
Vaccination		X			
Immediate surveillance (15 min)		X			
ARI surveillance^b		D14-D360			
Swab collection^b		D14-D360			
Study termination record					X
Collection of SAEs and AESIs^d	Throughout study				

AESI = adverse event of special interest, SAE = serious adverse event; ARI: acute respiratory infection

- Collection of the first blood sample to occur before vaccination, and may be taken at Screening or Visit 1 if the blood draw is not possible for one reason or another. The study team will make every effort to complete all blood-taking in one seating to avoid pricking the participants more than once.
- Subjects will be contacted weekly by SMS to record information about acute respiratory infections and prompted to collect a nasal swab if symptomatic.
- AESIs will have the same detailed information collected as SAEs. These include new onset of Guillain-Barré syndrome, encephalitis/myelitis (including transverse myelitis), Bell's palsy, optic neuritis, and brachial neuritis.

Study Name: Immunogenicity trial of 3 influenza vaccine [VAP3]

Protocol Number: 2021.247

DSRB Ref Number: 2022/00275

Version & date: version 2.0, dated 27 Oct 2022

Page 16 of 38

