8.3 SMS REMINDERS

Throughout the study, participants will be sent a weekly short message service (SMS) asking whether they have experienced an ARI (at least one acute respiratory symptom or sign and one systemic symptom) in the previous 7 days (Attachment 5). Responses will be recorded in the study database and used to calculate ARI risk in the cohort at the end of the study.

Participants will also receive SMS reminders about any follow-up appointments. The use of SMS reminders has been shown to improve retention in research studies [16]. The SMS reminder will include their appointment time and the location. Participants failing to attend their appointment will be contacted by phone to reschedule the appointment.

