8.5 RESPIRATORY SAMPLES

Participants will be provided with swab kits (swab plus vial of universal transport medium) at enrolment with instructions on how to use them (Attachment 6). During the 1-year follow-up period, if participants develop an ARI, they should perform a COVID-19 antigen rapid test (ART) and inform the study team within 24 hours of their ARI and COVID-19 ART result. Participants will be instructed to collect respiratory swab samples only if the COVID-19 ART is negative (Attachment 9). The study team will follow up with them to arrange for the respiratory swabs to be sent to the laboratory for influenza testing. Influenza-positive swabs will then be forwarded to the National Public Health Laboratory at NCID for virus characterization. Participants should store the respiratory samples in the home refrigerator until the study team collects them.

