The percentage of B memory phenotype (CD27+ and/or IgD-) cells that are HA probe reactive on d14 will be estimated for each vaccine arm, accounting for pre-vaccination percentage and vaccination history as described in 13.3. The HA probe cross-reactivity, isotype, and phenotype of HA reactive B cells for each vaccine group and time-point will be visually compared using t-distributed stochastic neighbor embedding (t-SNE), a statistical method for visualizing high-dimensional data by giving each datapoint a location in a two or three-dimensional map.

13.4.7 SECONDARY OBJECTIVE 6

To assess whether QIV-R offers better protection against infection compared with QIV-C or QIV-E.

Evidence of influenza infection will be based on RT-PCR-confirmed infection, only, as serological evidence may be biased in vaccinees who elicit a good antibody response to vaccination (22).

Attack rates will be calculated for each vaccination group as the number of cases during the person-time at risk. If there are sufficient cases, the proportion testing positive for each vaccine will be compared using logistic regression with influenza infection as 1 if test-positive and 0 if test-negative or not tested and no ARI. The explanatory variable will be the type of vaccine (1=QIV-R, 2=QIC-C, 3=QIV-E). Samples size permitting, we will also explore whether attack rates were associated with the post-vaccination GMT.

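### Section 13.4.7 gives no outcome value to a participant whose only ARI was not influenza-tested, which inflates the proportions testing positive, and its logistic model ignores follow-up time

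*Combined protocol and SAP*

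**What the plan says.** Section 13.4.7 fixes the case definition: "Evidence of influenza infection will be based on RT-PCR-confirmed infection, only". It then gives two measures. The first is a rate: "Attack rates will be calculated for each vaccination group as the number of cases during the person-time at risk". The second, to be run if there are enough cases, is a logistic regression of the proportion testing positive, with "influenza infection as 1 if test-positive and 0 if test-negative or not tested and no ARI". Vaccine enters as follows: "The explanatory variable will be the type of vaccine (1=QIV-R, 2=QIC-C, 3=QIV-E"). Section 13.4 adds vaccination history to every model.

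Who is tested depends on other sections. Section 8.5 states: "Participants will be instructed to collect respiratory swab samples only if the COVID-19 ART is negative". The footnote to the schedule in 7.3 carries no such condition: "Subjects will be contacted weekly by SMS to record information about acute respiratory infections and prompted to collect a nasal swab if symptomatic". ARIs are recorded separately from swabs, through a weekly message "asking whether they have experienced an ARI (at least one acute respiratory symptom or sign and one systemic symptom) in the previous 7 days" (8.3).

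Section 12.3, in the text on withdrawals, says in general terms that all participants will be part of the analyses.

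**The concern.** The coding rule covers three kinds of participant: positive on a swab, negative on a swab, and never tested with no ARI. It omits the participant who had an ARI and was never tested. Section 13.4.7 has no missing-data rule for this, so the outcome is undefined and the record would by default drop out of the logistic model. The ART rule in 8.5 makes this a regular occurrence. The weekly messages mean that such illnesses will be visible in the database without a swab result.

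The loss runs one way under the plan's own definition. A participant with a positive swab always stays, and those who leave all lack PCR confirmation. This bears on the trial's only comparison of protection against infection. If the same code is used for the infected-versus-uninfected titre comparison in 6.2.6, the uninfected group there would also be selected on illness and testing history.

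There is a second mismatch. The attack rate is defined over person-time, but the model that compares the arms has no follow-up time in it.

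**Working it through.** **Inputs.** There are 120 participants per arm (13.2), a case is RT-PCR-confirmed only (13.4.7), and swabs are taken only after a negative ART (8.5). The documents give no influenza risk, case count or rate of untested ARI for this objective, so there is no plan figure to reproduce. All risks and shares below are assumptions.

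**Step 1: who has a value.**

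| Participant's history | Value under 13.4.7 |
|---|---|
| A positive swab | 1 |
| Swabbed, no positive | 0 |
| Never swabbed, no ARI | 0 |
| Never swabbed, at least one ARI | none |

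The gap is per participant. Someone with an ART-positive illness and a second, swabbed illness can still be coded, although the plan has no rule for several episodes.

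**Step 2: proportions testing positive.** Let p be the risk of RT-PCR-confirmed influenza and u the share of unconfirmed participants without a value. Reported proportion = p / [p + (1 − p)(1 − u)]. With p = 3% and 120 per arm there are 3.6 cases and 116.4 non-cases.

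| u | Non-cases dropped | Reported proportion |
|---|---|---|
| 10% | 11.6 | 3.6 / 108.4 = 3.3% |
| 20% | 23.3 | 3.6 / 96.7 = 3.7% |
| 40% | 46.6 | 3.6 / 73.4 = 4.9% |

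At p = 10% and u = 30% the result is 0.10 / (0.10 + 0.90 × 0.70) = 13.7%.

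**Step 3: odds ratio.** Now let p be the risk of true influenza, c the share of participants without influenza who are uncoded, and m the share with influenza who are uncoded. The odds in an arm are p(1 − m) / [(1 − p)(1 − c)], so

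observed OR = true OR × [(1 − m_R)/(1 − m_E)] × [(1 − c_E)/(1 − c_R)].

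- Equal loss: with 10% (QIV-E) and 6% (QIV-R), the true OR is (0.06/0.94) / (0.10/0.90) = 0.574. With c = 30% in both arms and m = 0 it is [0.06/(0.94 × 0.70)] / [0.10/(0.90 × 0.70)] = 0.574, unchanged. The ratio of proportions moves from 0.600 to 0.610.
- Unequal loss: c = 30% (QIV-E) and 20% (QIV-R) gives a factor of 0.70/0.80 = 0.875. The reverse gives 0.80/0.70 = 1.143.
- Chance imbalance alone, simulated with equal c and about 110 non-cases per arm, gives a 95% range for the factor of 0.91 to 1.09 (c = 10%), 0.84 to 1.19 (c = 30%) and 0.77 to 1.31 (c = 50%).

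**Step 4: true infection rather than PCR-confirmed infection.** The reported proportion is p(1 − m) / [p(1 − m) + (1 − p)(1 − c)]. It equals p when m = c and falls below p when m > c. For example, p = 10%, c = 10% and m = 20% gives 0.08 / (0.08 + 0.81) = 9.0%. The inflation in step 2 is therefore relative to the plan's RT-PCR-only definition, not to all influenza.

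**Step 5: follow-up time.** Section 13.2 allows for 10% attrition, or 12 of 120 per arm. A participant lost early with no ARI on record is coded 0, exactly like one observed to the end of surveillance at D360 (7.3).

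**The case against.** The strongest reply is that the planned measure is an odds ratio, and step 3 shows that it does not move under equal loss. Allocation is randomised 1:1:1 within strata (9.2), participants wear an eye mask at injection (9.1), and the ART rule applies to every arm. A reader might infer that the vaccine comparison is distorted. The documents do not support that, because nothing in them suggests that untested ARI would differ systematically by vaccine. This part of the objection stands.

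Three other inferences also go too far.

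- A reader might take those who leave to be true non-cases. Their influenza status is unknown, and unswabbed influenza or co-infection with COVID-19 leaves as well.
- A reader might take every participant with a positive ART to be excluded. The gap concerns those with no influenza test at all.
- A reader might take the 1/2/3 coding as a linear term. It reads as labels for the type of vaccine, although 13.4.2 is clearer in naming separate parameters.

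The analysis is also secondary, conditional on enough cases, and imprecise. At an assumed 5% risk there are 6 cases and 114 non-cases per arm, so the standard error of the log odds ratio is √[2 × (1/6 + 1/114)] = 0.59. The 95% interval around 1.00 is then about 0.31 to 3.19, against which a factor of 0.875 is small. The person-time attack rates do not use the 0/1 code. The 7.3 footnote may simply abbreviate 8.5.

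This limits the size of the problem but does not close the gap. The coding still excludes participants after randomisation, contrary to 12.3, and the handling of untested ARI could still be chosen after the data are seen.

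**Conclusion.** The point holds in a limited form. The outcome in 13.4.7 is undefined for participants whose only ARI was untested, and 8.5 produces such participants by instruction. If they drop out, the proportions testing positive are too high relative to the plan's own case definition: 3.3% to 4.9% for an assumed 3%, with 10% to 40% of non-cases uncoded. The odds ratio is biased only if the loss differs by arm; a 10-point difference (20% v 30%) shifts it by about 12% to 14%. That difference is an assumption, so the finding is a risk to the comparison and not a demonstrated bias. Separately, the logistic model and the person-time attack rate in the same section measure different things. For a conditional secondary analysis this is worth correcting, but it does not threaten the trial's primary result.

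**What to change.** Rewrite the comparison in 13.4.7 as follows.

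- Include every vaccinated participant. The event is the first RT-PCR-confirmed influenza from D14, which also settles the handling of several episodes. Person-time runs from D14 to the event, withdrawal or last contact.
- Compare arms by Poisson regression with a log person-time offset, or by Cox regression. Use separate QIV-R and QIV-C indicators with QIV-E as reference, plus vaccination history. The condition on sufficient cases can stay.
- Report by arm the number of participants with an untested ARI and with an ART-positive ARI.
- Add a sensitivity analysis in which untested ARI is treated as missing or is imputed, with the assumptions stated.
- Reconcile the swab instructions in the 7.3 footnote and 8.5, so that it is clear which illnesses were meant to be tested.

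The cost is SAP wording, plus an alignment of two protocol passages. The analysis uses message, swab and visit dates already collected and does not affect recruitment. The drawback is that true influenza that was never tested counts as a non-case in the main analysis, which is why the counts by arm and the sensitivity analysis are needed.

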14 STORAGE OF BLOOD AND TISSUE SAMPLES

14.1.1 DETAILS OF WHERE SAMPLES WILL BE STORED, AND THE TYPE OF CONSENT FOR FUTURE USE OF SAMPLES

14.1.1.1 Serum samples storage and shipping

Blood samples collected in serum tubes will be centrifuged within 24 hours of collection to separate the clotted blood from the serum and the serum removed to a clean tube. The clotted blood may be discarded. Sera will be aliquoted into separate tubes, the number of which will depend on the volume recovered but is expected to be around 3 aliquots of approximately 500-1000µl each. One serum aliquot (~1 ml will be shipped to WHOCCRRI for serology). One will be stored at -20°C, while the remaining aliquots will be stored in a -70°C freezer or in liquid nitrogen. All freezers are locked and located in secured areas.

Written consent will also be obtained from participants for use of their samples for future studies. All participant information will be de-identified and a Human Research Ethics Committee would have to approve such future studies before stored samples can be analysed.

14.1.1.2 Peripheral Blood Mononucleocytes (PBMCs) storage and shipping

Blood samples collected in Sodium Heparin tubes will be processed for recovery of PBMCs on the same day or within 24 hours of collection. The recovered cells will be aliquoted in to ~4 tubes. Each aliquot will be labelled and cryogenically stored in liquid nitrogen at the recruitment site until the end of each study year. The cryogenic storage facility is in secured area at A*Star Infectious Disease Labs. Half of the aliquots for each sample will be shipped to WHOCCRRI for B cell analysis.

Respiratory swabs will be tested for influenza at the National Public Health Laboratory at NCID. Media from swabs that test positive for influenza virus will be aliquoted into two tubes and stored at -70C. One aliquot will be inoculated into established cell lines to obtain influenza isolates

Influenza isolates will be shipped to the WHOCCRRI for antigenic and genetic testing. Isolates will be assessed using antigenic assays such as the HI assay (see 10.2). Both original specimens and isolates may be genetically sequenced (note that viral RNA will be sequenced, not human DNA). Both the original specimen and any isolates recovered will be stored in -70°C freezers, according to NATA-approved SOPs at the WHOCCRRI. All freezers are locked and located in secured areas. Samples will be stored indefinitely using study numbers.

14.1.1.3 Consent to storage of specimens for future related research

Samples will be stored indefinitely and may be retested as new technologies for understanding immunological responses to respiratory virus infection and/or vaccination become available. During the informed consent process participants will be asked if their samples can be stored for future studies.

15 DATA SECURITY & HANDLING

15.1 DETAILS OF WHERE RECORDS WILL BE KEPT & HOW LONG WILL THEY BE STORED

Study Name: Immunogenicity trial of 3 influenza vaccine [VAP3]

Protocol Number: 2021.247

DSRB Ref Number: 2022/00275

Version & date: version 2.0, dated 27 Oct 2022

Page 34 of 38

15.1.1 STUDY DATABASE

A study database will be established and managed using the REDCap electronic data capture tool developed by Vanderbilt University and hosted at NCID. REDCap provides detailed information about the security measures they have taken to secure data storage <https://projectredcap.org/software/mobile-app/>. Briefly, data are transmitted using secure, encrypted transmission (SSL/HTTPS). Additional validation checks are also used when communicating with the server. The REDCap Mobile App employs encryption-at-rest on the mobile device's hard drive so that all important data and information stored on the device is properly protected from unauthorized or malicious users.

If during the course of the study it is determined that other software may better meet the needs of the study, the team may migrate the study database to different software.

15.1.2 DATA ENTRY

Data collected in questionnaire and generated from laboratory assays will be collected in paper form or electronically. Participants will be able to enter responses to the questionnaire directly using a mobile device. This will avoid the need for transcribing data from paper questionnaires and enable the use of validity checks to ensure that impossible or improbable entries are avoided. Paper questionnaires may also be used if there are technical issues at the study site. The project manager will enter the data into the study database.

15.1.3 DATA STORAGE

Hard copies of any information collected (e.g. informed consent) will be stored in locked filing cabinets in the PI's office. Electronic copies of data collected will be stored using the password protected study database.

All research data will be stored for a minimum of 15 years after completion of the project. After fifteen years electronic records will be erased unless further approval for retention is obtained. Individual participants will not be identifiable from the presented or published material. The PIs will be responsible for all data management.

15.2 CONFIDENTIALITY AND SECURITY

Participant confidentiality is strictly held in trust by the participating investigators, research staff, and the sponsoring institution and their agents. This confidentiality is extended to cover testing of biological samples in addition to the clinical information relating to participants. The study protocol, documentation, data and all other information generated will be held in strict confidence. No information concerning the study, or the data will be released to any unauthorized third party, without prior written approval of the sponsoring institution. Authorized representatives of the sponsoring institution may inspect all documents and records required to be maintained by the PI, including but not limited to, medical records (office, clinic or hospital). The clinical study site will permit access to such records. All laboratory specimens, evaluation forms, reports and other records that leave the site will be identified by the participant ID number only to maintain participant confidentiality. Clinical information will not be released without written permission of the participant, except as necessary for monitoring by HREC or regulatory agencies.

16 ATTACHMENTS

Document Name	Version Number	Date
1. Poster	V1.0	08 Jun 2022
2. NCID poster	V1.0	05 Aug 2022
3. CRF	V4.0	16 Sep 2022
4. ICF	V4.0	27 Oct 2022
5. Symptoms questionnaire	V1.0	15 Aug 2022
6. Nasal swab instructions	V1.0	10 Aug 2022
7. Acknowledgement form	V1.0	15 Aug 2022
8. Participant ID card	V1.0	06 Sep 2022
9. ARI reporting guide	V1.0	28 Sep 2022

